4.9.4. ECG

The ECG test includes heart rate, PR interval, QRS interval, QT interval, QTc interval using Bazett's formula, QTc interval using Fridericia's formula, and RR interval.

Summary statistics for actual values and change from baseline in each ECG parameter will be presented by study group and visit.

The number and percentage of subjects with shifts from normal to each of the categorical values denoting an abnormal scan (abnormal not AE, abnormal AE) will be summarized by study group. A listing of subjects with abnormal status in ECG will be presented.

QTc (interval using Fridericia's formula) will also be examined to determine the incidence of clinically relevant abnormalities. The number of subjects evaluated and the number of subjects with clinically relevant abnormalities will be presented. The criteria for clinically relevant post-dosing abnormalities are:

- Maximum increase from baseline QTcF > 30 to 60 ms
- Maximum increase from baseline QTcF > 60 ms
- Maximum post-baseline QTcF > 480 to 500 ms
- Maximum post-baseline QTcF > 500 ms

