8.2. Exclusion Criteria

Candidates will be excluded from study entry if any of the following exclusion criteria exist at Screening, or at the timepoint specified in the individual criterion listed:

CONFIDENTIAL

The information contained herein may not be used, disclosed, or published without the written consent of Biogen MA Inc.

Medical History

1. History of drug abuse or alcoholism within 6 months before study enrollment that would limit participation in the study, as determined by the Investigator.
2. Presence of an untreated or inadequately treated active infection requiring systemic antiviral or antimicrobial therapy, or any other ongoing medical condition during the screening period that, according to the Investigator, would interfere with the conduct or assessments of the study.
3. Significant cognitive impairment, clinical dementia, or unstable psychiatric illness, including psychosis, suicidal ideation, suicide attempt, or untreated major depression ≤ 90 days, as determined by the Investigator.
4. History of allergies to a broad range of anesthetics.
5. Presence of risk for increased or uncontrolled bleeding and/or risk of bleeding that is not managed optimally and could place a participant at an increased risk for bleeding during or after an LP procedure. These risks could include, but are not limited to, anatomical factors at or near the LP site (e.g., vascular abnormalities, neoplasms, or other abnormalities) and underlying disorders of the coagulation cascade, platelet function, or platelet count (e.g., hemophilia, Von Willebrand's disease, liver disease).
6. Presence of an implanted shunt for the drainage of CSF or an implanted CNS catheter.
7. Clinically significant abnormalities in hematology or clinical chemistry parameters, as determined by the Investigator, which would render the participant unsuitable for enrollment.
8. Clinically significant, as determined by the Investigator, 12-lead ECG abnormalities, including corrected QT interval using Fridericia's correction method of > 450 ms for males and > 470 ms for females.

Medications

9. Prior or current treatment with small interfering RNA, stem cell therapy, or gene therapy.
10. Treatment with another investigational drug, biological agent (excluding BIIB067), or device within 1 month or 5 half-lives of study agent, whichever is longer.
11. Current or anticipated need, in the opinion of the Investigator, of a DPS during the study period.

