16.6.2.6. Electrocardiogram

The changes from baseline will be summarized using shift tables. The number and percentage of participants with shifts to the categorical values (abnormal, not AE; or abnormal and AE) will also be summarized.

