4.9.1. Adverse Events

All AEs will be classified using MedDRA version 27.0 or later. All AEs will be listed but only treatment emergent AEs will be summarized, where treatment emergence will be relative to the first dose of study drug. A treatment emergent AE/SAE is defined as any AE/SAE with an onset date and time that is on or after the first dose of study drug or any pre-existing condition that has worsened in severity after the first dose of study drug. In case of missing dates,

- Any AE/SAE with both a missing onset date and resolution date, or any AE/SAE with a missing onset date and a resolution date which is after the first dose of study drug, will be considered treatment emergent.
- If the onset date is available but onset time is missing and the AE onset date is the same as the first dose date the AE will be considered treatment emergent.
- For AEs with a partial start date, the year/month of the event date will be compared to that of the first dose date to determine whether the event is treatment emergent.

The incidence of treatment emergent AEs will be summarized by study group as follows:

- by primary system organ class (SOC) and MedDRA preferred term sorted by decreasing frequency
- by SOC and MedDRA preferred term sorted by alphabetical order
- by MedDRA preferred term
- by SOC

- The most common treatment emergent AEs i.e. occurring in $\geq 5\%$ subjects in any study group will be presented by MedDRA preferred term.
- For Part C subjects only, the most common treatment emergent AEs i.e. occurring in 2 or more subjects in subjects previously on tofersen in 233AS101 compared to subjects who were on placebo will be presented by MedDRA preferred term.
- By maximum CTCAE grade, primary SOC and MedDRA preferred term
- By maximum CTCAE grade and MedDRA preferred term
- AEs with a CTCAE grade ≥ 3 by primary SOC and MedDRA preferred term
- Related AEs by primary SOC and MedDRA preferred term
- SAEs by primary SOC and MedDRA preferred term
- SAEs by MedDRA preferred term
- Related SAEs by primary SOC and MedDRA preferred term
- AEs related to lumbar puncture (as assessed by the investigator) by primary SOC and MedDRA preferred term
- AEs that occurred within 24 hours of dosing by primary SOC and MedDRA preferred term (in case of partial AE start date, if the month and year are available and day is missing, the AE will be included for any dose that occurs in the same month and year as the AE)

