Each hematology, blood chemistry, coagulation and CSF laboratory parameter will be flagged as “low” or “high” relative to the parameter’s normal range or as “unknown” if no result is available. For each urinalysis laboratory parameter, the number and percentage of subjects experiencing post-dosing shifts to abnormal will be summarized. For each hematology, blood chemistry, coagulation and CSF parameter, the number and percentage of subjects experiencing post-dosing shifts to ‘low’ or ‘high’ will be summarized. In each summary, the denominator for the percentage is the number of subjects at risk for the shift. The number at risk for the shift to low is the number of subjects whose baseline value was not low and who had at least one post-baseline value. The number at risk for the shift to high is the number of subjects whose baseline value was not high and who had at least one post-baseline value. Subjects will be counted only once for each parameter and each shift regardless of how many post-dosing assessments had that type of shift. Subjects with shift will be listed by laboratory parameter and shift type. All postbaseline data will be used in the shift tables, regardless of whether a scheduled or unscheduled visit. For CSF laboratory parameters, both tubes will be used in this assessment for the shift tables.

Summary statistics for actual values and change from baseline in laboratory values will be summarized by dose group and visit. Line plots for chemistry, hematology and CSF showing mean value for each dose group at each visit will also be presented.

To evaluate potential serious hepatotoxicity subjects with a post-baseline AST and/or ALT value ≥ 3 times the upper limit of normal (ULN) and a post-baseline bilirubin value >2 times ULN at any time, not necessarily concurrent, will be listed with their values. In addition, a plot will be presented with each subject’s maximum post-baseline AST or ALT value relative to the ULN against the subject’s maximum post-baseline bilirubin value relative to the ULN; values do not have to be concurrent. All postbaseline data will be used in the shift tables, regardless of whether a scheduled or unscheduled visit.

Listings of all chemistry, hematology, coagulation, CSF, urinalysis values and pregnancy test (serum and urine) will be provided. Abnormal values and potentially clinically significant values will be flagged.

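### SAP 4.9.4 counts ECG category shifts only from a normal baseline, so worsening from *abnormal not AE* to *abnormal AE* is missing from the ECG shift summary that the protocol planned

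*SAP*

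**What the plan says.** Protocol 16.6.2.6 makes two statements about ECG. The first is "The changes from baseline will be summarized using shift tables". The second is "The number and percentage of participants with shifts to the categorical values (abnormal, not AE; or abnormal and AE) will also be summarized". Neither restricts the category from which a shift starts.

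SAP 4.9.4 implements this as the number and percentage with "shifts from normal to each of the categorical values denoting an abnormal scan (abnormal not AE, abnormal AE", by study group. It describes no other ECG shift table and gives no denominator for the percentage. Its remaining ECG outputs are summary statistics for each parameter (values and change from baseline), four QTcF outlier criteria, and a listing: "A listing of subjects with abnormal status in ECG will be presented".

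SAP Section 5 declares two departures from the protocol: efficacy and biomarker analyses move to the integrated report, and the enriched/other presentation is dropped. The ECG restriction is not among them. The list of changes for version 4.0 in SAP 6.1 does not mention ECG either.

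**The concern.** The two abnormal categories are graded by consequence: one is an abnormal scan not judged an AE, the other is an abnormal scan that is an AE. Moving from the first to the second is a worsening that a safety reader would expect a shift table to show. The SAP wording leaves it out, while counting the milder move from normal to *abnormal not AE*.

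Such participants can be in the study. Exclusion criterion 8 in Protocol 8.2 removes "Clinically significant, as determined by the Investigator, 12-lead ECG abnormalities", so a scan that is abnormal but not clinically significant does not bar entry. Baseline is also not drug-free for everyone. The SAP Introduction notes that some Part C participants arrive after approximately 6 months of tofersen. An ECG that became abnormal in Study 233AS101 would count as an abnormal baseline here.

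At stake is the completeness of the one planned categorical summary of change in overall ECG reading, in a final standalone report that the SAP says will focus on safety and exposure.

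**Working it through.** The plan states no figure on this point, so the check compares the texts and enumerates the possible moves. Three states are used: N (normal), A (*abnormal not AE*) and E (*abnormal AE*).

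**Step 1. Moves into an abnormal category.** Three states give six possible changes. Two of them (A to N, E to N) end in normal. The other four end in A or E:

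| Move | Within Protocol 16.6.2.6 (no stated starting category) | Counted by SAP 4.9.4 (from normal only) |
|---|---|---|
| N to A | yes | yes |
| N to E | yes | yes |
| A to E | yes | no |
| E to A | yes | no |

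The SAP covers two of the four. Of the two it omits, E to A is an improvement and A to E is a worsening. A to E is the one that matters for safety.

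**Step 2. Can A to E occur?** Yes, because criterion 8 permits an A scan at entry. The documents do not report how many participants have one.

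**Step 3. Is the move captured elsewhere?**
- *AE tables (SAP 4.9.1).* A treatment-emergent AE includes "any pre-existing condition that has worsened in severity after the first dose of study drug". The event can therefore be counted by system organ class, preferred term, grade, relatedness and seriousness, and in the incidence-rate tables. None of these shows a change in ECG status from baseline.
- *Listing (SAP 4.9.4).* The participant's abnormal scan is listed, but a listing gives no number or percentage who worsened.
- *QTcF criteria (SAP 4.9.4).* These apply whatever the baseline category, but only to QTc.

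The event can thus be visible in the report, but none of these outputs supplies the missing cell.

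**Step 4. Is the departure declared?** No, neither in SAP Section 5 nor in SAP 6.1.

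**Step 5. How many participants?** This cannot be derived. It needs the share with an A scan at baseline and their risk of moving to E, and neither is given. Any percentage would only restate the values assumed for those two inputs.

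**The case against.** The strongest reply is that the gap is one cell in a secondary descriptive table. A scan classed as *abnormal AE* is by its label an adverse event, and AEs are counted in full as the primary endpoint. That stands. A reader might infer that the event goes uncounted altogether, or that the number of new ECG-related AEs is understated overall. The documents support neither reading, because the treatment-emergent definition takes in worsened pre-existing conditions. The omission is confined to the ECG shift summary.

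A second reply is that the protocol is silent on the starting category, so a shift to abnormal could mean a shift from not-abnormal, which the SAP merely spells out. This is possible. It fits less well with the protocol's first sentence, which calls for shift tables of changes from baseline, and with its naming of two separate abnormal end categories. At the least, the SAP has chosen the narrower reading without saying so.

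A third reply concerns the laboratory rule in SAP 4.9.2: "The number at risk for the shift to low is the number of subjects whose baseline value was not low". It is tempting to cite this as proof that the SAP contradicts itself. It is only a partial analogy. It does define the at-risk group by the target category rather than by normality, and it states a denominator, which the ECG section does not. But low and high are opposite directions, not ordered grades, so the rule says nothing about worsening within an abnormal state.

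Finally, scheduled ECGs under protocol version 6 are confined to Screening, Day 1 and the Final or Early Termination Visit, with others at the investigator's discretion. That limits the data. It does not remove the issue, because SAP Table 2 shows that dosing-visit ECGs were dropped only at version 6, so earlier versions supplied more post-baseline scans.

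**Conclusion.** The point holds for the ECG shift summary. SAP 4.9.4 restricts the count to participants with a normal baseline, Protocol 16.6.2.6 does not, and the narrowing is undeclared. Followed literally, the SAP rule leaves out a worsening from *abnormal not AE* to *abnormal AE*.

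The impact is modest. The table is descriptive, no decision rests on it, and the primary endpoint is unaffected. The number of participants concerned is unknown and could be none. The conclusion assumes that the SAP wording will be programmed as written and that the protocol's silence on the starting category means no restriction. It is still worth correcting, because the stated rule produces an incomplete count and the data to complete it are already collected.

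**What to change.** In SAP 4.9.4, replace the from-normal wording with a shift table by study group that crosses baseline category (normal / *abnormal not AE* / *abnormal AE* / missing) with post-baseline category. Count shifts to *abnormal AE* among all participants whose baseline was not already *abnormal AE*, and state that group as the denominator. Where a participant has several post-baseline scans, say which one classifies the participant; the protocol leaves this open.

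If the sponsor prefers to keep the narrower count, SAP Section 5 should declare and justify it. That would settle the undeclared departure but leave the worsening out of the table.

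The cost is a short change of wording and one table shell, with no new data. The count of shifts to *abnormal AE* may become slightly less favourable.

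### The QTcF outlier table in SAP 4.9.4 has no absolute category between the protocol's entry limit (450 ms men, 470 ms women) and 480 ms, so values there with a rise of 30 ms or less enter no QTcF category

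*SAP*

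**What the plan says.** SAP 4.9.4 sets four criteria for clinically relevant QTcF abnormalities after dosing:

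- The lower of two categories for the rise is "Maximum increase from baseline QTcF > 30 to 60 ms".
- The upper, open-ended one for the rise is "Maximum increase from baseline QTcF > 60 ms".
- The lower of two categories for the absolute value is "Maximum post-baseline QTcF > 480 to 500 ms".
- The upper, open-ended one for the absolute value is "Maximum post-baseline QTcF > 500 ms".

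The absolute criteria start above 480 ms and are the same for both sexes.

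The same section plans three other ECG outputs. These are summary statistics for each parameter by study group and visit, a count described as "The number and percentage of subjects with shifts from normal to each of the categorical values denoting an abnormal scan", and a listing of subjects whose ECG status is abnormal.

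Protocol 8.2, exclusion criterion 8, concerns "Clinically significant, as determined by the Investigator, 12-lead ECG abnormalities" and gives as an included case "corrected QT interval using Fridericia's correction method of > 450 ms for males and > 470 ms for females". The lead-in to the list fixes when it applies: "Candidates will be excluded from study entry if any of the following exclusion criteria exist at Screening". Individual criteria may name another time point. Protocol 16.6.2.6 plans ECG shift tables and sets no QTcF cut-off for analysis.

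**The concern.** The protocol regards a QTcF above 450 ms in a man, or above 470 ms in a woman, as enough to question entry. The SAP's lowest absolute outlier category lies 30 ms higher for men and 10 ms higher for women. A subject who enters within the limit, crosses it on treatment and stays at or below 480 ms is in the QTcF table only if the rise exceeds 30 ms.

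Safety is the primary objective, and SAP section 1 says that the final standalone analysis concentrates on safety and exposure. What is at stake is whether this QTcF table is complete at its lower end. No efficacy conclusion and no decision rule depends on it.

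**Working it through.** The plan gives no figure to reproduce; this is a check of which values the four criteria cover.

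**Inputs**

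| Input | Value | Source |
|---|---|---|
| Rise categories | >30 to 60 ms; >60 ms | SAP 4.9.4 |
| Absolute categories | >480 to 500 ms; >500 ms | SAP 4.9.4 |
| Entry limit L | 450 ms men; 470 ms women | Protocol 8.2, criterion 8 |
| Baseline | closest value before first dose in 233AS102 | SAP 3.1 |

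**Rule.** Let b be baseline and m the maximum post-baseline QTcF, so the maximum rise is m − b. A subject meets none of the four criteria exactly when m ≤ 480 and m − b ≤ 30, that is, when m ≤ min(480, b + 30).

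**Above the entry limit.** The uncounted range is L < m ≤ min(480, b + 30). It exists only if b > L − 30:

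- Men: b > 450 − 30 = 420 ms. The range is widest at b = 450, from above 450 to 480 ms (30 ms).
- Women: b > 470 − 30 = 440 ms. The full range, above 470 to 480 ms (10 ms), is reached from b = 450 upward.

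**Examples**

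| Subject | Baseline | Maximum | Rise | QTcF category |
|---|---|---|---|---|
| Man | 445 | 470 | 25 | none |
| Man | 450 | 480 | 30 | none |
| Woman | 465 | 478 | 13 | none |
| Man | 419 | 451 | 32 | rise >30 to 60 |

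**Grid check.** Take whole-millisecond pairs with baseline from 360 ms to L and maximum from L + 1 to 560 ms.

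- Men: baselines 421 to 450 give 1, 2, …, 30 uncounted pairs, so 30 × 31 / 2 = 465.
- Women: baselines 441 to 450 give 10 × 11 / 2 = 55, and baselines 451 to 470 give 20 × 10 = 200, in total 255.

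Adding a category from L to 480 ms brings both to 0, by construction. These are combinations of values, not patients.

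**Where the man at 445 then 470 ms appears.** He contributes to the by-visit statistics, which under SAP 4.1 generally include the maximum, but these give no subject count. He is in the shift table only if his baseline scan was read as normal and a later one as abnormal. He is in the listing only if a scan was read as abnormal. If his scans are read as normal, he is in no categorical ECG count and not in the planned ECG listing.

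**Baseline reset.** SAP section 1 says that some Part C subjects have had about 6 months of tofersen before entry. If such a subject's QTcF had already risen by x ms, a further 25 ms makes x + 25 in total, but the table sees 25. For any x above 5 the total exceeds 30 ms and the rise category is still not met. The documents do not give x, and it may be zero. Absolute categories do not depend on baseline, but they begin above 480 ms.

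**The case against.** The strongest objection is that the two thresholds do different jobs. Criterion 8 decides who may enter and leaves room for the investigator's judgement. It was never set as a limit for on-treatment tabulation, and the SAP's four QTcF categories already go beyond what Protocol 16.6.2.6 requires. This stands. A reader might infer that the SAP contradicts the protocol, but the documents do not support that.

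A reader might also infer that these cases are never counted, or that nothing at or below 480 ms is. Neither follows. Rises above 30 ms count at any absolute level, and a scan read as abnormal can reach the shift table and the listing. Those routes do not replace a QTcF count, however. They depend on an overall reading of the ECG, and the shift count omits anyone whose baseline scan was already abnormal.

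Nor should the point rest on sparse ECG data. SAP 2.3 (Table 2) shows that ECGs left the dosing visits only with protocol version 6, and the version 6 amendment summary shows that triplicate recordings became single at the same time. Subjects followed under earlier versions can have many post-baseline ECGs. This cuts the other way too: a low cut-off applied to a maximum over many visits, with no concurrent control, will collect some chance crossings. That is a fair limit on how the new row can be read.

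Finally, nothing in the documents says that a QT effect, if any, would be mild. The point does not need that claim.

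**Conclusion.** The gap is real but small: above 450 to 480 ms in men and above 470 to 480 ms in women, with a rise of 30 ms or less. For subjects within the limit at baseline, it needs a baseline above 420 ms (men) or above 440 ms (women). How many subjects fall there is unknown, because the documents give no QTcF distribution. The rise categories protect least in the prior-tofersen Part C group, because its baseline is taken on treatment.

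The conclusion rests on reading the four criteria as written and on baseline as defined in SAP 3.1. It does not assume that tofersen affects QTcF. This is a cheap improvement in the completeness of a safety table and no more.

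The SAP already reports lower tiers elsewhere: systolic pressure above 140 and above 160 mmHg, diastolic above 90 and above 100 mmHg (4.9.3), and CSF leukocytes above 5 and above 10 (4.9.2).

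**What to change.** Add one row to the QTcF table in SAP 4.9.4: maximum post-baseline QTcF above 450 to 480 ms for men and above 470 to 480 ms for women. Show it twice: for all subjects with a post-baseline QTcF, and for those among them whose baseline was at or below the limit for their sex. The second version separates new crossings from values already high at baseline, as the at-risk denominators in SAP 4.9.2 do for laboratory shifts.

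Add a footnote that the row is descriptive, takes the maximum over a number of ECGs that varies by subject and protocol version, and has no concurrent control.

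The cost is one row and a footnote. It needs no new data, and it changes neither the entry criterion nor patient management.
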